1.2.4.2 Vitamin D reverses MTB-induced phagocyte maturation arrest

Antimycobacterial activity of vitamin D_3 is further demonstrated by studies of phagolysosome function. An important mechanism of MTB immune evasion is inhibition of phagocyte maturation. Killing of phagocytosed organisms is usually achieved through a calcium-dependent fusion process between phagosomes and toxic acid-containing lysosomes(45). By inhibiting the fusion step, through inhibition of sphingosine kinase(45), MTB is able to achieve latency in a protected niche. Hmama and colleagues have demonstrated that MTB-induced phagocyte maturation arrest in a human macrophage model is able to be reversed by vitamin D_3 , via a PI3-K pathway(46). This finding, and those of Sly et al., implicate PI3-K as an important mediator of the antimycobacterial action of vitamin D_3 , and provide an example of non-genomic (VDR independent) signaling of vitamin $D_3(41)$.

1.2.4.3 TLR activation triggers vitamin D-mediated MTB immune response; adequate responses require serum vitamin D sufficiency

In their seminal 2006 *Science* paper, Liu et al. demonstrated that TLR1/2 activation of human macrophages (an MTB-induced process in vivo) upregulated the expression of both the vitamin D receptor and 1 α -hydroxylase genes, resulting in increased production of the antimicrobial peptide cathelicidin, with subsequent intracellular killing of MTB(47). Thus a second mechanism of vitamin D₃-mediated mycobacterial killing, in this instance utilizing genomic VDR-mediated responses, has been identified.

The researchers went on to demonstrate that successful induction of antimycobacterial activity through cathelicidin production was reliant upon replete serum vitamin D levels. Serum from ethnic groups (African Americans) at higher risk for TB had lower levels of $25(OH)D_3$, and their serum was less efficient in supporting cathelicidin mRNA induction; supplementation of this serum with $25(OH)D_3$ restored TLR-induction of cathelicidin mRNA. The findings provide an immunological basis for differential susceptibility among human populations to mycobacterial infection; namely, that vitamin D deficiency appears to portend higher risk of TB disease.

1.2.4.4 Epidemiological and clinical evidence for the importance of vitamin D in TB outcomes

Prior to the antibiotic era, nutritional supplementation (including vitamin D-rich cod liver oil) and sunlight exposure were centrepieces of therapy for TB(48-50). Finsen was awarded the Nobel Prize for Medicine in 1903 for demonstrating the use of light exposure (which acts by upregulating vitamin D production) to treat lupus vulgaris (cutaneous tuberculosis)(51). Deficiency of vitamin D has been demonstrated in people with TB(52), and in ethnic groups recognised to be at higher risk for TB(47), including darkly-pigmented migrants to cooler climates(53). who have elevated risk of development of

active TB post-migration. Vitamin D receptor polymorphisms have been found to be under-represented in pulmonary TB patients(54) (and in lepromatous leprosy)(55), suggesting the importance of vitamin D-mediated pathways in determining TB susceptibility, although meta-analysis of VDR polymorphisms has been inconclusive(56).

Martineau and colleagues(57) identified and reviewed three RCTs and ten prospective case series in which vitamin D was administered to patients with TB; most were conducted in the 1950s, were identified as being of poor quality, and used vitamin D₂, were identified as being of poor quality, and used Ergocalciferol (vitamin D_2), which is known to be less efficacious than cholecalciferol (D_3)(58). Only one study investigated the impact of vitamin D supplementation on TB outcome, and although concluding that vitamin D was beneficial, there were no statistically significant differences in clinical response(59). A more recent trial of vitamin D supplementation in Indonesian pulmonary TB patients appeared to be safe, and suggested more rapid sputum clearance and radiological improvement(60), but the trial was small and the process of randomisation was not described. A larger study with rigorous randomisation is required, such as we propose. Liu et al. and Martineau et al. advocate trials of vitamin D supplementation in patients with TB(47), particularly those with vitamin D insufficiency. A study conducted in Surabaya found that three quarters of patients with TB, and the same proportion of control subjects without TB, had serum vitamin D levels of less than 21 ng/mL (=80 nmol/L)(61), consistent with vitamin D deficiency according to latest recommended reference ranges(62). A recent position statement on vitamin D supplementation emphasised that even in countries with apparent high ambient UV light, vitamin D remains a common and under-diagnosed problem(63).

1.2.5 Do macrophages kill MTB by predominantly NO- or Vit D-mediated mechanisms? Do the L-arginine-NO and Vitamin D-cathelicidin pathways interact?

A major debate is ongoing about the fundamental biology of the mechanisms by which human macrophages kill intracellular pathogens such as MTB(47). While rodent models have identified NO as the central mechanism for mycobacterial killing by macrophages and protection from tissue destruction, Liu et al. have postulated that these NO-mediated mechanisms are more important in nocturnal animals such as mice than in diurnal animals such as humans who are able to synthesise vitamin D_3 in the skin on exposure to UV light. Nathan has argued that the limitations of current *in vitro* and *ex vivo* models for inducing human iNOS and testing its role in mycobacterial killing mean we cannot exclude a major role for NO in humans(64). We have shown that notwithstanding the difficulties in inducing NOS2 in vitro, human monocytes/macrophages are capable of high level NOS2 expression in vivo, and that NO production/PBMC NOS2 expression is associated with protection from infectious disease in humans(20).

There are evident intersections between these two immunological pathways. Firstly, CYP27B1, the gene which encodes 1α -hydroxylase (the enzyme which converts 25-hydroxyvitamin D₃ to the biologically active form of vitamin D₃, 1,25-dihydroxyvitamin D₃) gene, requires an extracellular source of L-arginine for full expression, and is upregulated by NO in an avian macrophage cell line(65-67). Secondly, the antimycobacterial effect of vitamin D may be mediated in part by NO.(43, 68) The inhibitory effect of Vitamin D₃ on MTB in cultured human macrophage cell lines was initially thought to be mediated by NO upregulation, as demonstrated by Rockett and colleagues(43), but subsequent studies did not replicate this finding, as described in Section 1.2.4.1. However more recent work by Martineau and colleagues gives support to Rockett's finding that vitamin D₃, when added to MTB-infected cultured human peripheral blood mononuclear cells, did upregulate NOS2a expression, but the effect was small in comparison with the strong upregulating impact of vitamin D₃ on the antimicrobial

peptide cathelicidin(68), which is emerging as an important mediator of anti-TB immunity in humans(47).

Those on both sides of this deabte acknowledge the difficulty of answering this question with current *in vitro* tools(47, 64). Our clinical trial is designed to determine the potential utility of L-arginine and Vitamin D as adjuvant therapies. An additional benefit of our study will be the comparison of the *in vivo* potency of these two major candidate immune pathways of mycobacterial killing in humans in clearing mycobacteria from sputum and ameliorating pathology. As well as the potential for clinical and public health benefit, this study will contribute to the understanding of the biological mechanisms of disease protection in human TB relative to mouse models.

2 TRIAL HYPOTHESES AND OBJECTIVES

2.1 Hypotheses

- L-arginine supplementation in pulmonary TB will be safe, will increase plasma arginine concentrations, will enhance pulmonary production of nitric oxide (NO) (a key arginine-dependent immunomodulator and downstream immune mediator of mycobacterial killing) and will improve the rapidity and magnitude of the microbiological and clinical response. Baseline pulmonary NO production will be elevated in pulmonary TB but inversely associated with disease severity. Both baseline and post-treatment increments in exhaled NO will be associated with rapidity and magnitude of the treatment response.
- 2) Supplementation with vitamin D, the metabolite of which (1,25-dihydroxyvitamin D₃) has antimycobacterial activity, will be safe, will increase plasma Vitamin D concentrations, and will improve the rapidity and magnitude of the treatment response in human PTB.

2.2 Aims

- 1) Determine whether supplementation with L-arginine and / or vitamin D is safe and results in more rapid improvement in clinical, mycobacterial, immunological, radiological, physiological and functional measures of treatment outcome. We will randomise patients with pulmonary TB to receive, in addition to standard TB therapy, adjuvant arginine, vitamin D, arginine and vitamin D, or placebo. We will relate serial measurements of plasma concentrations of L-arginine and vitamin D, and immunological responses (pulmonary NO production, T cell function and phenotype) to measures of treatment outcome [mycobacterial (sputum smear clearance and culture conversion), physiological (spirometry), clinical (symptoms and weight), radiological (chest Xray) and functional (six-minute walk test, modified St George Respiratory Questionnaire)].
- 2) Determine whether expired NO is inversely related to disease severity at presentation. Baseline and serial measures of NO production will be correlated with disease severity and the magnitude and rapidity of clinical response.

3 TRIAL METHODS

3.1 Setting

The study will be based at the Timika TB Clinic and community health centre (Puskesmas) and the community hospital, Rumah Sakit Mitra Masyarakat (RSMM), Timika, Papua Province, Indonesia.

3.2 Study Population

Patients diagnosed with pulmonary TB at RSMM, the Timika TB clinic or the Timika Puskesmas will be eligible to enrol in the study. All patients with suspected TB will be diagnosed in the usual way according to the NTP guidelines. This will include three sputum smears examined for acid fast bacilli and a chest Xray. During the study period, surveillance and evaluation of extrapulmonary TB cases will

also take place (Appendix 10).

3.2.1 Inclusion criteria

Adults 15 years of age or older will be recruited if they have sputum smear positive pulmonary TB; have never received more that one month of anti-TB treatment in the past (that is, only new cases of TB will be included); agree to continue treatment in Timika for the full six month course of treatment; are not pregnant, and consent to enrol in the study.

3.2.2 Exclusion Criteria

Children less than 15 years of age, TB patients who have previously received treatment for TB for more than one month, patients unwilling to continue treatment in Timika for the full course, pregnant patients and those who are not willing to enrol in the study, will be excluded. Patients will be excluded from the study if hypercalcaemia (ionized calcium >1.32 mmol/L) is identified at baseline.

3.3 Interventions

3.3.1 Informed consent

All patients will receive a detailed explanation regarding the reason for the study and what it involves, and regarding the voluntary nature of involvement in the study. Each eligible patient will be provided with verbal and written information in Bahasa Indonesia, or verbally using a Papuan translator if required.

Only patients who understand the study and provide informed consent will be enrolled. It will be explicitly stated that involvement is voluntary, participants are able to say no, and if they do initially consent, they can leave the study at any time they wish without prejudicing their treatment in any way. On withdrawing from the study, the researchers will provide ongoing positive encouragement and support for the participants to continue her/his TB treatment as usual, according to the National TB Protocol.

3.3.2 Enrolment Procedure

All patients with confirmed smear positive pulmonary TB will be provided by the Research Assistant (RA) with verbal and written information in Bahasa Indonesia (see Patient Information Sheet, Appendix 3) regarding ADAPT, and informed consent will be obtained prior to patient enrolment. For participants who cannot read the information sheet and consent form, the study will be carefully and fully explained using a Papuan translator if required. Consenting participants will then receive their randomisation assignation. To achieve this, an envelope will be opened containing the code (Study Identification (ID) Number) assigning the patient to an unidentified (blinded) study arm. The Study ID Number will match a numbered Study Drug Packet containing the study drugs (see also Section 7).

Before any medications are administered, the baseline blood sample will be collected (see below) for immediate calcium results, along with the evaluations listed below (section 3.3.3.1). The first supervised dose of TB medication plus study drugs will then be administered. The patient name, time

of randomisation, the randomisation number, and whether or not they were excluded from the vitamin D/placebo arm will all be noted.

All patients will be required to attend the clinic daily during the intensive phase and twice a month for the continuation phase to receive their anti-TB medications, study medications, routine examinations and the study examinations as outlined below (Follow up, section 3.3.5).

3.3.3 Study Medications

3.3.3.1 Medication administration

At enrolment, patients will be randomly assigned to one of three groups:

- 1) Group 1: supplementary **L-arginine** 6g daily for eight weeks plus **placebo vitamin D**₃ once every four weeks for two doses (0 and 4 weeks);
- Group 2: supplementary L-arginine 6g daily for eight weeks plus vitamin D₃ (cholecalciferol) 50 000 IU (1250mcg) once every four weeks for two doses (0 and 4 weeks);
- Group 3: placebo L-arginine daily for eight weeks plus vitamin D₃ (cholecalciferol) 50 000 IU (1250mcg) once every four weeks for two doses (0 and 4 weeks);
- Group 4: placebo L-arginine daily for eight weeks plus placebo vitamin D₃ every four weeks for two doses (0 and 4 weeks);

Study drugs will be administered separately from the pre-packaged TB medications, provided in standard Indonesian NTP 'Combipacks' (fixed dose combination therapy for TB).

3.3.3.2 L-Arginine

L-arginine hydrochloride powder is commercially available as a GMP standard nutritional supplement (Nutricia Hong Kong). It will be compounded into a 6g dose at RSMM pharmacy. A matching placebo from the same manufacturer with identical appearance, colour, size, and taste will also be prepared.

The study medication will then be packaged and numbered according to the randomisation sequence. Clearly marked Study Drug Packs will be stored in a cool, dry place in the medication cupboards of the Timika TB Clinic and RSMM.

The choice of 6g daily is based on clinical experience with this dose, safety profile at this and higher doses, and the need to adhere to a once daily regimen for TB patients to avoid dosing errors (all other medications are dosed once daily), and to optimise adherence.

3.3.3.3 Vitamin D_3 (Cholecalciferol)

We will use high dose vitamin D_3 (Calciferol Strong, 50 000 IU cholecalciferol; PSM Healthcare, Auckland, NZ), a formulation that allows monthly oral administration. This will be given orally at baseline and again at 4 and 8 weeks. Matching placebo will similarly be obtained. This is similar to but lower dose than standard stoss therapy (intermittent high dose depot vitamin D dosing) used for restoration of vitamin D deficiency(70). The large volume of distribution of vitamin D (since it is fat soluble) necessitates such large doses before any change in plasma vitamin D level is detectable.

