Sputum collections will be obtained at baseline from each TB patient in accordance with NTP standard protocols (minimum of 2 positive smears) prior to enrolment in the study. An additional sputum specimen will be obtained on the day of entry into the study. The study sputum specimen containers will be distinct from standard sterile specimen jars used at the clinic or hospital, and will be labelled with the patient's details (name, study ID number, age, sex), date of collection and laboratory number. A microscopy slide will be prepared from this specimen and examined using standard Zeihl Neelsen method, labelled using a diamond-tipped pen as above and stored at the NIHRD-MSHR Research Building for later QA. Sputum specimens will be divided to provide material for smear examination, antigen testing, culture, susceptibility testing and MIRU typing as detailed in Appendix 15.

11) Blood collection

Twenty mL venous blood (a safe amount) will be collected from participants at enrolment and at follow up weeks 2, 4, 8 and 24 as described in Appendix 15.

12) Urine Collection

A midstream urine specimen will be collected into a sterile specimen container for TB antigen testing as detailed in Appendix 15.

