6 ASSESSMENT OF SAFETY

6.1 Intervention Procedure

Potential adverse effects of L-arginine and vitamin D will be carefully monitored. Adverse effects from oral L-arginine are uncommon.(27) Use of up to 21g daily was not associated with adverse events in two studies(28, 74). Oral L-arginine 7g three times daily for 4 weeks was associated with diarrhoea in 3 of 27 patients, but this resolved on dose reduction to 7g twice daily(75). Minor gastrointestinal discomfort has been reported in up to 3% of patients(27, 76). We do not expect that this will be a problem but will monitor our study patients carefully for this adverse effect and treat accordingly.

Although much less common than in other granulomatous diseases, vitamin D supplementation in TB has the potential for hypercalcaemia from extra-renal $1,25(OH)_2D_3$ production(77). Based on our previous experience with vitamin D supplementation ([name], personal communication), and extensive review of the literature(60, 78-81), the risk of symptomatic hypercalcaemia as a complication of vitamin D supplementation at the dose proposed in this study(63) in patients with pulmonary TB is anticipated to be very low. Ionised calcium will be measured, using portable i-STAT cartridges in Timika, at 0, 2, 4 and 8 weeks. In the unlikely event of hypercalcaemia developing, the literature indicates that the most likely time of onset would be 2-4 weeks post commencement of anti-TB therapy. Patients found to have elevated *i*Ca²⁺ on follow up will have their Vit D/placebo dose withheld.

6.2 **TB Medication side effects**

All patients with pulmonary TB in the study will be treated with anti-tuberculous agents according to the standard NTP protocol. This comprises daily weight-adjusted doses of Rifampicin (R), Isoniazid (H), Pyrazinamide (Z) and Ethambutol (E). Medications are taken under direct observation by health care workers during the intensive phase. Treating doctors will comply with NTP guidelines with regards to standard monitoring for TB drug side effects.

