11. Waktu pengam (dicatat juga di tab What time was blood taken (writ	ung)	:8	jam	Minggu 0,2,4,8,24 : ambil darah Weeks 0,2,4,8,24: take blood
12. Catat hasil pen	neriksaan darah i	STAT:		
Write iSTAT blood results	Ionised calcium		mmol/L	
	Creatinine		mmol/L	
	Haemoglobin		g/dL	
13. Jika ada hasil p relevan:	pemeriksaan dara	ah yang		Ingat !! penyimpanan sampel darah
If any other relevant / abnormal	blood tests are available, wri Uric acid	te results here:	mg/dL	Keep remainder of blood for storage * record any adverse events
	ALT		u/L	
	Other			
	Other			
	Other			

[figure not shown]
Code : TAD- |__|_|_|

Tolong tuliskan no. kartu TB dari respondent yang bersangkutan disetiap halaman formulir ini

14. BTA AFB	$ \begin{array}{c} 1 \\ 2 \\ 3 \\ 4 \\ 5 \\ 6 \end{array} $	0 Scanty 1+ 2+ 3+ 4+	Setiap minggu sampai minggu ke 8, dan minggu ke 24, Pemeriksaan dahak mikroskopis Every week until week 8, then week 24, collect sputum for microscopy and indicate result
15. eNO: jam		ppb	Minggu 0 , 2 ,4, 8, 24: Periksa NO dan tulis hasil
16. Selama minggu lalu, berapa kali minum obat sirup During the last week, how many doses of study medication were taken?	$ \begin{array}{c} 0\\ 1\\ 2\\ 3\\ 4\\ 5\\ 6\\ 7\\ 7 \end{array} $	0 1 2 3 4 5 6 7 Don't know	Berikan makanan ringan kepada pasien Give patient a snack Berikan pengobatan studi (obat sirup setiap minggu mulai minggu 0 – 8, obat tablet hanya pada minggu 0 dan 4) Give study medications (arg every week, D only week 0 and 4)
17. Berat badan		kg	
18. Height		m	Omit if already done in previous week and not
 19. Tes jalan 6 menit ^{6-min walk test} 20. Tes fungsi paru 		m	growing MINGGU 0,4,8,24: Lakukan tes jalan 6 menit dan catat jarak tempuh jalan: Weeks 0,4,8,24 : Do 6-min walk test Lakukan tes fungsi paru
Lung function tests		L/s	dan catat hasil
FVC		L	
21. Kuisioner Respiratori St George	Ya 🗌 1	Tidak 📃 2	MINGGU 0,4,8,24: Interview and isi kuisioner Respiratori St George
SGRQ done yes / no 22. Foto rontgen	Ya 🗌	Tidak 🗌 2	MINGGU 0,8, 24: CXR

Code : TAD- |__|_|_|_

Tolong tuliskan no. kartu TB dari respondent yang bersangkutan disetiap halaman formulir ini

NIHRD_MSHR Health Research Collaboration ADAPT study Study HREC Number 07/40

ADAPT	•	e : TAD- _	_
Tolong tuliskan no. kartu TB dari respondent yang ber	sangkutan dise	etiap halaman form	ulir ini
Gg. Pendengaran	Ya 🗌	Tidak 🔤 2	
Gangguan penglihatan	Ya 🗌	Tidak 🔤 2	
Poor vision, colour blind Gangguan persendian	Ya 🗌	Tidak 🗌 2	

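### The protocol gives two vitamin D3/placebo doses (weeks 0 and 4) in two places and three (weeks 0, 4 and 8) in a third, so cumulative exposure is not fixed

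*Protocol*

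**What the plan says.** Three places in the protocol give the vitamin D schedule.

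- Section 3.3.3.1, which defines the arms, gives vitamin D3 or its placebo "once every four weeks for two doses (0 and 4 weeks". Group 4 is worded slightly differently but has the same two time points.
- Section 3.3.3.3, the section on the vitamin D product, says: "This will be given orally at baseline and again at 4 and 8 weeks".
- The weekly form in Appendix 2 tells staff: "Give study medications (arg every week, D only week 0 and 4". The Indonesian text beside it says the same.

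Three further provisions depend on the schedule. Section 6.1 states: "Ionised calcium will be measured, using portable i-STAT cartridges in Timika, at 0, 2, 4 and 8 weeks". It also says that patients with raised calcium "on follow up will have their Vit D/placebo dose withheld". Study blood, under section 3.3.4.1, "will be collected from participants at enrolment and at follow up weeks 2, 4, 8 and 24".

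**The concern.** The number of doses is part of the definition of a randomised treatment. It determines what goes into each pre-numbered pack, what staff hand out at the week-8 visit, and what a report can say was tested. Someone packing from section 3.3.3.3 and someone dosing from the Appendix 2 form would be working to different schedules. Placebo is involved as well, because the matching placebo must follow the same schedule for blinding to hold.

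The safety text also presupposes one schedule. Section 3.3.3.4 cancels any later vitamin D dose after hypercalcaemia. Appendix 15 has staff wait for the calcium result and take the vitamin D or placebo out of the packet if it is high. At week 8 these rules have a dose to act on only if there is a third dose.

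**Working it through.** **The texts side by side**

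| Place | Doses | Weeks |
|---|---|---|
| Section 3.3.3.1, all four groups | 2 | 0, 4 |
| Appendix 2, weekly form | 2 | 0, 4 |
| Section 3.3.3.3 | 3 | 0, 4, 8 |

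All three are complete sentences or instructions in current text. They are not table fragments, and they do not come from a change log. The dose count is stated rather than derived, so there is no figure of the plan's to reproduce.

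**Cumulative dose.** The amount per dose is 50 000 IU (1250 mcg), from section 3.3.3.1, and section 3.3.3.3 gives the same 50 000 IU.

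- Two doses: 2 × 50 000 = 100 000 IU (2 × 1250 = 2500 mcg).
- Three doses: 3 × 50 000 = 150 000 IU (3 × 1250 = 3750 mcg).
- Ratio: 150 000 / 100 000 = 1.5, or 50% more.

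**Participants concerned.** Groups 2 and 3 receive active vitamin D, with 111 per arm (section 5.1): 2 × 111 = 222. The other 222 receive vitamin D placebo on the same schedule.

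**Calcium tests after the last dose.** Section 6.1 lists weeks 0, 2, 4 and 8. In the Appendix 2 visit table, blood is crossed out at weeks 12, 16 and 20 and open at week 24.

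- Two doses: the last dose is at week 4 and the next scheduled calcium is at week 8, so the interval is 8 − 4 = 4 weeks.
- Three doses: the last dose is at week 8, the visit of the last calcium test in section 6.1. No later test is listed there. The next study blood is at week 24, so the interval is at least 24 − 8 = 16 weeks. Section 6.1 does not list calcium at week 24, but the form has a calcium field linked to the blood draws, which include week 24.

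The follow-up table in section 3.3.5 has a row for calcium, but its shading is not legible in the text available. It was not used.

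**What does not change.** The number of doses does not enter the sample-size calculation. As a side check, take 111 × 0.9 ≈ 100 evaluable per arm, 60% against 40%, two-sided 5%. In a simple two-arm comparison the power is Φ[(0.20 − 1.96 × √(2 × 0.5 × 0.5/100)) / √((0.24 + 0.24)/100)] = Φ[(0.20 − 0.1386)/0.0693] = Φ(0.886) ≈ 81.2%, close to the stated 82%. This is not the graphical factorial method that the protocol used. It only shows that no dosing term is involved. The 1-month culture precedes week 8, so a third dose cannot act on it.

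**The case against.** The strongest reply is that little is really open. Two places out of three agree, and they are the arm definitions and the form that staff use. Packs are prepared from one randomisation sequence, and the dosing staff have one instruction in two languages. This has some weight, but it does not settle the matter. The text that differs is the section devoted to the drug, and no order of precedence is stated.

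The reply is stronger against three readings that go further.

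- A reader might infer that calcium monitoring is undefined. It is not: section 6.1 fixes it "at 0, 2, 4 and 8 weeks". The only open question is whether those times extend past the last dose.
- A reader might infer that, with three doses, nobody is checked for hypercalcaemia for 16 weeks. The documents do not support this. The side-effect table in Appendix 5 calls for ionised calcium in response to several symptoms, including nausea, constipation, polyuria and confusion. The weekly form keeps the symptom review open at weeks 12, 16 and 20, and section 3.3.2 has patients attending twice a month in the continuation phase. Section 6.1 also expects hypercalcaemia most often 2 to 4 weeks after TB treatment starts, a window that the week-2 and week-4 tests cover under either schedule. What remains is the absence of a scheduled test.
- A reader might infer that participants in the same arm will receive different exposure. A mismatch between pack and form makes this possible, but nothing shows that it would happen. A uniform surplus or shortage is just as plausible.

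**Conclusion.** The contradiction stands. Whether there is a week-8 vitamin D3/placebo dose is not determined by the protocol, and the cumulative active dose is therefore 100 000 or 150 000 IU for 222 participants, assuming 111 per arm as planned. It would be too broad to say that the experimental treatment as a whole is undefined. The amount per dose, the first two dose times and the arginine regimen do not conflict in these sections.

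The calcium gap is a conditional consequence and not a second error. It arises only under the three-dose reading, and it concerns scheduled tests only.

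Sample size, power and the 1-month culture outcome are unaffected. A week-8 dose could bear on safety and on assessments made after it, such as 6-month lung function. Whether it could bear on the secondary outcome of change in 25(OH)D depends on the time point used, which section 4.2 does not state. The case for correcting this before enrolment rests on the dosing conflict alone: it is a rule that the trial acts on, through packs made up in advance.

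**What to change.** Before any packs are made up, reconcile section 3.3.3.1, section 3.3.3.3, Appendix 2 and the contents of the numbered Study Drug Packs, active and placebo, to a single vitamin D schedule. Then check that the calcium schedule in section 6.1 and the blood draws in Appendix 2 are consistent with it, including whether calcium is meant to be measured at week 24. Which schedule is right, and what monitoring goes with it, is for the investigators to decide.

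The cost is a wording correction and a pack check before the first patient. The sample size and the primary analysis need no change.
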